Title: Penicillin De-Labeling in the Pediatric Primary Care Setting; Protocol

NCT Number: 05010304

IRB Approval Date: 11/29/2021

PROTOCOL FORM / RESEARCH DESCRIPTION

If an item does not apply to your research project, indicate that the question is "not applicable" – do not leave sections blank

Click once on the highlighted entry in each box to provide your response. Click the item number/letter or word, if hyperlinked, for detailed instructions for that question. If your response requires inserting a table, picture, etc, you may need to first delete the box that surrounds the answer and then insert your table or other special document.

1. Purpose and objectives. *List the purpose and objectives:*

The goal of this project is to explore the feasibility of implementing a penicillin allergy delabeling protocol for low-risk pediatric patients in the primary care setting. Specifically, we seek to demonstrate risk-stratification of reported adverse reactions to penicillins and completion of direct amoxicillin challenge in low-risk subjects can be performed in the outpatient pediatric primary care setting.

2. Background.

- Describe past experimental and/or clinical findings leading to the formulation of your study.
- For research involving investigational drugs, describe the previously conducted animal and human studies.
- For research that involves FDA approved drugs or devices, describe the FDA approved uses of this drug/device in relation to your protocol.
- Attach a copy of the approved labeling as a product package insert or from the Physician's Desk Reference.

You may reference sponsor's full protocol or grant application (section number and/or title) or if none, ensure background includes references.

Please respond to all components of this item, or clearly indicate which components are not applicable.

a. Background

Reported adverse drug reactions to penicillins are common; however, more than 90% of patients with a penicillin allergy label can safely tolerate penicillins (1, 2). Numerous adverse

outcomes are associated with an unverified penicillin allergy, and elective evaluation for penicillin allergy has been recommended (1, 3, 4).

There is a vast disparity between the number of patients with a penicillin allergy label and practicing allergists in the United States, with over 30 million penicillin-allergic labeled patients and less than 5000 practicing allergists (5, 6). With such a significant prevalence of labeled penicillin allergy, no single medical discipline can handle this burden alone; a coordinated effort across both primary care and subspecialists will be required to address this. As the majority of penicillin allergy labels occur in young childhood, pediatricians are uniquely situated to have a significant impact in reducing the long-term consequences of a penicillin allergy label through delabeling strategies (1, 5). Direct oral challenge in low-risk patients has been recommended as a delabeling strategy for this population (7-9). Cumulative studies have now evaluated the safety and efficacy of direct amoxicillin challenge in children with a penicillin-allergy label in over 1400 subjects (8-16); the majority of studies have taken place in the outpatient allergist setting. Across studies, positive challenge rates ranging from 0-13%. The largest study was a single center prospective study which defined low-risk allergy patients as an absence of severe cutaneous adverse reactions (SCARs); they reported on 818 patients and found a 6% positive challenge rate (8). Across the above studies, all reactions were mild and only required treatment with oral antihistamines, no epinephrine use was documented in any of these studies.

While there is significant evidence for the safety and efficacy of direct penicillin challenge in the evaluation of penicillin allergy, this has not yet been widely implemented in the primary care setting. There have been two pilot studies exploring direct amoxicillin challenge in the pediatric primary care setting. The first was a retrospective study of 42 children in Australia who included children greater than 18 months old. They performed direct amoxicillin challenges after 3 months had elapsed from the index reaction. There was a 3% positive challenge rate and all reactions resolved with only oral diphenhydramine. The second was a prospective study that included 102 children in Ireland and there were no positive challenges to amoxicillin challenge. This approach has not been studied in the United States. A recent survey of US-based pediatricians identified perceived barriers to implementing penicillin allergy evaluations into their routine care (17). Significant gaps in knowledge exist regarding the feasibility of this approach involving direct amoxicillin challenge procedures in low-risk patients in the pediatric primary care setting.

4. Joint Task Force on Practice P, American Academy of Allergy A, Immunology, American College of Allergy A, Immunology, Joint Council of Allergy A, et al. Drug allergy: an updated practice parameter. *Ann Allergy Asthma Immunol.* 2010;105(4):259-73.
6. American Academy of Allergy Asthma and Immunology Report on the Allergy and Immunology Physician Workforce (1999-2009/10). Rensselaer, NY: The Center for Health Workforce Studies; 2012 [Available from: <https://www.aaaai.org/Aaaaai/media/MediaLibrary/PDF%20Documents/Practice%20and%20Parameters/2012-AI- Physician-Workforce-Report.pdf>].

Currently there is no standard protocol in the Children's Health pediatric primary care clinic for evaluation of penicillin-allergy labels. Most often, children with a penicillin allergy label are referred to the Children's Health pediatric allergy clinic for evaluation of penicillin allergy regardless of their risk status based on the history of their index reaction to penicillin.

3. Study Design.

Describe the study design (e.g., single/double blind, parallel, crossover, etc.) Consider inserting a scheme to visually present the study design.

This study is a prospective, descriptive, single arm study of a convenience sample of children from age 2-18 with a history of parent reported penicillin allergy who present to an outpatient pediatric clinic for a routine healthcare maintenance visit.

4. Research Plan / Description of the Research Methods:

4.a. Provide a comprehensive narrative describing the research methods.

- 1) Provide the **order in which tests/procedures will be performed**,
- 2) Provide the **setting** for these events and a description of the **methods used to protect privacy** during the study.
- 3) Provide the **plan for data analysis** (include as applicable the **sample size calculation**)

Please respond to all components of this item, or clearly indicate which components are not applicable.

Patients will be recruited from the pediatric primary care clinic at the Children's Health Specialty Center Dallas campus who are scheduled for a routine healthcare maintenance visit, have a penicillin allergy listed in the electronic medical record, and have consented to participate in research activities. Patient caregivers will receive a telephone call, where in a study member will introduce the topic of penicillin allergy and delabeling through direct

amoxicillin challenge and obtain verbal consent to administer a risk-stratifying questionnaire evaluating the index reaction and their interest in proceeding with the amoxicillin challenge, including reasons for hesitancy and perceived barriers. Subjects with a history of reactions consistent with severe cutaneous adverse reactions will be excluded. The study member will review the oral amoxicillin challenge procedure and assess caregiver and patient's interest in proceeding with oral amoxicillin challenge.

Subjects who are classified as low-risk and are interested to proceed with direct amoxicillin challenge will be sent the consent form through the caregiver's preference of encrypted email, mail, or patient portal MyChart for their review. Caregivers will be provided the option to sign the electronic consent form, using an encrypted, secure platform provided through UTSW (DocuSign/REDCap), and if they choose this option, will be contacted via telephone to review the consent form and answer applicable questions. Alternatively, when presenting for their healthcare maintenance visit at the pediatric primary care clinic at the Children's Health Specialty Center Dallas campus, the written consent form will be reviewed.. Patients will be screened for acute dermatitis or respiratory symptoms. Subjects with acute dermatitis or respiratory symptoms at time of evaluation will be excluded. A point of care urine pregnancy test will be performed on adolescent female subjects who have begun menstruation; subjects who have a positive pregnancy test or who are breastfeeding will be excluded.

A single dose of amoxicillin 50 mg will be administered at the start of the healthcare maintenance visit. Subjects will be observed for 10 minutes and if no reaction, will be given a second 200 mg dose and observed for a further 50 minutes for immediate reactions, defined as onset of urticaria, angioedema, cough, wheezing, rhinitis, repetitive vomiting, diarrhea, protracted abdominal pain, or hypotension, and managed accordingly. This direct amoxicillin challenge testing is the recommended evaluation for low-risk patients, and the investigatory component of this study is if it can be performed in conjunction with a routine healthcare maintenance visit in the pediatric primary care setting. During this observation period, subjects will have their healthcare maintenance visit with the primary pediatric provider. Subjects who have a negative oral challenge will be provided documentation of their immediate tolerance of penicillin. Upon completion of challenge, a survey will be administered to families to assess the quality of their experience and identify areas for improvement. If immunizations are indicated per the CDC vaccination schedule, they will be administered after this 60-minute period of observation from the challenge. Subjects will be discharged with instructions to contact the pediatrician and study team for any delayed symptoms. We will also measure the duration of each subject's time in the clinic from check in to check out. A follow up encounter will occur over the phone at 7-10 days after the date of oral challenge to assess for delayed reactions. At 1 year post-challenge, subjects' penicillin allergy status will be assessed in the electronic medical record, and patients who have had penicillin allergy label added back to their allergy list will be contacted via telephone to assess reasons for the

addition of the penicillin allergy label. Descriptive statistics will be used to describe the population completing amoxicillin challenge testing.

4.b. List of the study intervention(s) being tested or evaluated under this protocol			
 N/A - this study does not test or evaluate an intervention. Skip to item 4.d.			
#	Study intervention(s) being tested or evaluated under the protocol Add or delete rows as needed	Affiliate Place a check next to institution(s) where the intervention will be performed	Local Standard Practice? Indicate whether the intervention is considered acceptable practice locally for applicable institutions
1	Direct Amoxicillin challenge	 UTSW	 Yes
		 PHHS	 Yes
		 CMC	 Yes
		 THR	 Yes
		 TSRH	 Yes
		 Other: _____	 Yes
2	Insert study intervention 2 here	 UTSW	 Yes
		 PHHS	 Yes
		 CMC	 Yes
		 THR	 Yes
		 TSRH	 Yes
		 Other: _____	 Yes

4.c. Risk:Benefit Analysis of study interventions being tested or evaluated under this protocol

For each study intervention identified in section 6b above, complete a risk:benefit analysis table.

(Two tables are provided, copy & paste additional tables as needed or delete both tables if this study does not test an intervention)

4.c.**Study Intervention #1**

Direct Amoxicillin Challenge

List each group exposed to this intervention on a separate line. (e.g., experimental, control, Arm A, Arm B, etc) Or state All Groups/Subjects	For each group, list the benefits of this intervention. (Benefits can be directly from the intervention or from a monitoring procedure likely to contribute to the subject's well being). If there are no benefits, state "none".
All groups/subjects	One benefit will be the accurate diagnosis of current penicillin tolerance status. If penicillin tolerant, would have the benefit of using penicillin-based antibiotic treatment for future infections and diminishing the harms associated with a penicillin-allergy label which include prolonged hospital stays, increased surgical site infections, increased rates of Clostridium Difficile infections, and increased healthcare utilization costs when compared to patients without a penicillin allergy label. Another benefit includes increased access to evaluation, as this evaluation would be included within patients' healthcare maintenance visit and not require a separate referral to an allergist with the associated barriers of time and cost with seeing another provider.

If you are requesting a Waiver of Informed Consent, complete the table below.

If you have a consent form, **list the reasonably foreseeable [risks](#) in the consent form (and do not complete this section).**

List the risks according to the probability (likely, less likely or rare) and magnitude (serious or not serious).

(include: 1) expected adverse events; 2) rare and serious adverse events; 3) all other psychological, social, legal harms)

Do not delete frequency. Frequency must be estimated because it will assist you with determining which adverse events will require prompt reporting.

	Not serious	Serious
Likely These risks are expected to occur in more than 20 out of 100 subjects.	•	•
Less likely These risks are expected to occur in 5-20 subjects or less out of 100 subjects.	•	•
		Serious

Rare These risks are expected to occur in less than 5 subjects out of 100		•	
--	--	---	--

4.c. Study Intervention #1 Insert name used in 4.b.	
List each group exposed to this intervention on a separate line. (e.g., experimental, control, Arm A, Arm B, etc)	For each group, list the benefits of this intervention. (Benefits can be directly from the intervention or from a monitoring procedure likely to contribute to the subject's well being). If there are no benefits, state "none".
Or state All Groups/Subjects	

If you are requesting a Waiver of Informed Consent, complete the table below.

If you have a consent form, list the reasonably foreseeable **risks** in the consent form (and do not complete this section).

List the risks according to the probability (likely, less likely or rare) and magnitude (serious or not serious).

(include: 1) expected adverse events; 2) rare and serious adverse events; 3) all other psychological, social, legal harms)

Do not delete frequency. Frequency must be estimated because it will assist you with determining which adverse events will require prompt reporting.

	Not serious	Serious
Likely These risks are expected to occur in more than 20 out of 100 subjects.	•	•
Less likely These risks are expected to occur in 5-20 subjects or less out of 100 subjects.	•	•
		Serious
Rare These risks are expected to occur in less than 5 subjects out of 100		•

		
4.d. List ALL other research procedures or components not listed in table 4.b.
 
The combination of Tables 4b and 4d should account for all of the research procedures that will take place during this study.
 
Consider grouping similar procedures under a single component (e.g., blood work, CT = safety assessments)
		
#	Research component	Column A	Column B	Column D
	
 individual procedures 
example:
 
Eligibility Assessments
 
 History and physical Questionnaire Laboratory tests 
Add or delete rows as needed
	
Local Standard Practice Indicate the number of times each procedure will be performed as stipulated in the research plan that would be performed if the participant were not participating in the study.
	
Research Only
 
Indicate the number of times each procedure will be performed solely for research purposes (meaning that the participant would not undergo the same number of procedures or would not undergo the procedure(s) at the same frequency if they were not participating in the study)
	
Risks
 
If you are requesting a Waiver of Informed Consent, complete the table below.
 
List the reasonably expected risks for each procedure or group of procedures under the following categories as appropriate:
 
 • Serious and likely; • Serious and less likely; • Serious and rare; • Not serious and likely; • Not serious and less likely
1	Eligibility Assessments			
	Questionnaire assessing Index Reaction and hesitancy and barriers to pursuing challenge		1	Not Serious and Less Likely
2	Healthcare Maintenance Visit			
	History and Physical	1		Not Serious and Less Likely
	Insert procedure here			
	Insert procedure here			
3	Post-challenge Assessment			
	Questionnaire assessing post-challenge status		1	Not Serious and Less Likely
	Insert procedure here			
	Insert procedure here			

4	Urine Pregnancy Test		1	Not Serious and Less Likely
	Insert procedure here			
	Insert procedure here			
	Insert procedure here			

5. Safety Precautions. (Describe safeguards to address the serious risks listed above.)

a. Describe the procedures for protecting against or minimizing any potential risks for each of the more than minimal risk research procedures listed above.

NA

b. Where appropriate, discuss provisions for ensuring necessary medical or professional intervention in the event of adverse events, or unanticipated problems involving subjects.

Risks of Protocol Specified Medications/Procedures

- Adverse reactions to amoxicillin include headache, diarrhea, nausea, vomiting, rash, and allergic reactions. Allergic reactions range from mild to severe, and if a patient has an allergic reaction, he/she may need oral, IM, or IV medications. The site investigators for this trial are credentialed advanced health providers who are trained to recognize and manage systemic reactions. Treatment will be available within 60 seconds in the event of a reaction. Emergency medications as listed below will be available to treat any allergic reactions.
- Treatment of individual acute allergic reactions during the conduct of the study may include antihistamines, epinephrine, β -adrenergic agonists, oxygen. The risks of these common medications include the following
 - o Antihistamines: drowsiness, dizziness, constipation, stomach upset, blurred vision, dry mouth/nose/throat
 - o Epinephrine: tachycardia, palpitations, nervousness, sweating, nausea, vomiting, trouble breathing, headache, dizziness, anxiety, tremors, pale skin
 - o β -adrenergic agonists: nervousness, shaking, headache, dizziness
 - o These risks will be minimized by appropriate dosing per guideline management of systemic allergic reactions.

c. Will the safeguards be different between/among groups?

Yes

No

If yes, describe here

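### Section 3 declares a convenience sample although the schedule and record imply a list to call from, so interest, uptake and completion are at avoidable risk of selection bias

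*Combined protocol and SAP*

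**What the plan says.** Section 1 gives the goal as to "explore the feasibility of implementing a penicillin allergy delabeling protocol for low-risk pediatric patients in the primary care setting". The specific objective covers risk stratification and completion of the challenge in low-risk children. It sets no rate, denominator or threshold.

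Section 3 calls the study a "single arm study of a convenience sample of children". The children are aged 2 to 18, their allergy is reported by a parent, and they are seen at a routine visit. This is the only statement of sampling method in the plan.

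Section 4.a draws patients from one clinic who are "scheduled for a routine healthcare maintenance visit, have a penicillin allergy listed in the electronic medical record". A further condition is that they "have consented to participate in research activities". It does not say when or how that consent is obtained. On contact it states: "Patient caregivers will receive a telephone call". The call covers the index reaction, interest in the challenge, and reasons for hesitancy and perceived barriers.

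Section 4.a closes with its only analysis statement: descriptive statistics on those who complete the challenge. No sample size is given.

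**The concern.** A convenience sample is easiest to defend when nobody can say in advance who is eligible. Here the visit is booked, the label is on file and contact is by telephone, so the eligible families can be listed before the first call.

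The plan neither uses such a list nor says how families are picked from it. If those called differ in willingness from those not called, the share interested, the share taking up the challenge and the share completing it describe the families called rather than the clinic's eligible children. For a study of feasibility, these are proportions a reader will look for. An analysis confined to completers would not reveal the problem, and counting afterwards cannot supply the answers of families who were never called.

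**Working it through.** The plan states no uptake, precision or sample size figure, so there is nothing to reproduce. The check has a textual part and an illustration.

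**1. Is there a list?** Section 4.a uses two conditions that clinic systems hold before contact, a scheduled visit and a recorded allergy, plus research consent. The text mentions no list; its existence follows from these conditions. Section 3 defines the allergy as parent-reported, whereas section 4.a uses "have a penicillin allergy listed in the electronic medical record". The list can be built from the second definition.

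**2. Is there a selection rule?** Section 4.a says caregivers are telephoned. It does not say that all, consecutive or randomly ordered families are called, nor that only some are. No number of attempts is set. No log is required of those eligible, called, reached, low-risk, interested, consented and completed.

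**3. Which results are exposed?** Completion is in the section 1 objective, and interest and hesitancy are asked of everyone reached. Both depend on who is called.

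**4. Illustration (every input is an assumption).** Let uptake be 70% in easy-to-reach families and 40% in the rest, let *s* be the easy share of the list, and let 80% of the sample be easy families.

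- Uptake over the whole list = *s* × 0.70 + (1 − *s*) × 0.40
- Uptake in the sample = 0.80 × 0.70 + 0.20 × 0.40 = 0.56 + 0.08 = 0.64

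| *s* | List uptake | Sample uptake | Overstatement |
|---|---|---|---|
| 0.3 | 0.21 + 0.28 = 0.49 | 0.64 | 15 points |
| 0.5 | 0.35 + 0.20 = 0.55 | 0.64 | 9 points |
| 0.7 | 0.49 + 0.12 = 0.61 | 0.64 | 3 points |

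**5. When the bias vanishes or reverses.** If a share *f* of the list is called, with uptake *p*c in called families and *p*n in the others, then bias = (1 − *f*) × (*p*c − *p*n). With assumed values *p*c = 50% and *p*n = 30%:

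- *f* = 0.3: 0.7 × 20 = 14 points
- *f* = 0.5: 0.5 × 20 = 10 points
- *f* = 0.7: 0.3 × 20 = 6 points
- *f* = 0.9: 0.1 × 20 = 2 points
- *f* = 1: 0

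The bias is also 0 at any *f* if the two groups are alike, and it is negative if the called families are the less willing ones.

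**6. Cost of the fix on the inputs of step 4.** Moving from 64% to 49-61% uptake gives 0.49/0.64 = 0.77 to 0.61/0.64 = 0.95 of the children per family called, or 5-23% fewer. Keeping the same number of children would need 0.64/0.61 = 1.05 to 0.64/0.49 = 1.31 times as many families called, or 5-31% more.

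**The case against.** The strongest defence is that the documents never say staff pick and choose. The sentence on telephone calls fits calling every eligible family, in which case convenience would describe only the single clinic and the visit type. This stands: selective calling is a possibility, not a documented practice. A reader might infer that section 3 lets staff favour willing families and that the results are therefore inflated, but the text supports neither step. Equally, nothing in the plan requires everyone to be called.

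Second, no uptake endpoint is defined. Section 4.a gives the investigational question as whether the challenge can be done alongside a routine visit, and it also collects reactions, clinic time, family experience and label status at one year. It would be too strong to call uptake and completion the study's results. They are quantities that the objective and the questionnaire invite the team to report, without a denominator.

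Third, ordered calling does not remove selection through prior research consent, being reached, or interest. That is correct. The last two are worth measuring as part of feasibility. Research consent remains a limit on who is represented.

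Fourth, the sampling method is openly declared and is common in a single-centre descriptive study that tests no hypothesis. That lowers the weight of the point. It does not explain why a weaker method is kept where a better one is within reach.

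**Conclusion.** The point holds as an avoidable risk. The plan states a convenience sample where an enumerable list is implied, gives no calling rule, and analyses completers only. Any interest, uptake or completion proportion would therefore carry a selection effect that could be neither ruled out nor assessed.

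Its size and direction cannot be established from the documents. The 3-15 points rest on assumed uptake of 70% and 40%, an easy share of 30-70% of the list, and a sample that is 80% easy families. A reader might infer 9-21 points (0.70 − 0.61 to 0.70 − 0.49), but that requires a sample made up entirely of easy families, which nothing in the plan suggests. If every listed family is already called, the bias from choosing whom to call is zero, and only the label and the missing flow report need attention.

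The change is worth making before recruitment, because it removes the one layer of selection under the study team's control.

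**What to change.** Replace the convenience-sample wording in section 3, and add to section 4.a, text such as: *Each week the clinic will list all children scheduled for a health maintenance visit who have a recorded penicillin label and whose families have consented to research activities. All listed families will be called. Where call capacity does not allow this, families will be called in order of appointment time or of a random number, with the same maximum number of attempts for each.*

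Add to the analysis statement that the numbers eligible, called, reached, low-risk, interested, consented and completed will be reported, with the denominator given for each proportion. Align the allergy definitions in sections 3 and 4.a so that the list has one definition.

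The cost is small but not nil: a few sentences and a log, and possibly fewer children per family called, some additional call attempts, and a less favourable reported uptake. It might be inferred that calls, staff and number of children all stay the same. That cannot hold if the bias is real, since lower uptake means fewer children from the same families called. No stated sample size would be missed as a result. Selection through prior research consent remains and should be reported as a limitation.

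### The 1-year record review cannot tell a label that stayed off from an allergy list nobody opened again, so the re-labeling proportion may be understated

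*Combined protocol and SAP*

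**What the plan says.** The 1-year follow-up is described near the end of the narrative in Section 4.a: "At 1 year post-challenge, subjects' penicillin allergy status will be assessed in the electronic medical record". The same sentence limits further contact to one group: "patients who have had penicillin allergy label added back to their allergy list will be contacted via telephone", to learn why. Subjects whose record shows no label are not contacted.

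The only other contact planned after the visit comes much earlier and has another purpose: "A follow up encounter will occur over the phone at 7-10 days after the date of oral challenge to assess for delayed reactions".

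The analysis plan is one sentence: "Descriptive statistics will be used to describe the population completing amoxicillin challenge testing". It gives no denominator for the 1-year status, no category for unknown status, and no requirement that the record was used after the challenge.

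Two features of the population bear on the point. Section 3 describes a "convenience sample of children from age 2-18 with a history of parent reported penicillin allergy", and Section 4.a draws subjects from one site: "Patients will be recruited from the pediatric primary care clinic at the Children's Health Specialty Center Dallas campus". Neither section says which other sites write to the electronic record.

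**The concern.** An allergy list changes only when someone edits it. A child who moves away, changes provider or is simply not seen again keeps the list as it stood after the challenge. At 1 year that list reads the same as one that was reviewed and found still clear. Contact is triggered only by finding a label, so nothing in the plan would reveal the difference.

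If such children are counted as label off, subjects in whom a re-label may not be observable sit in the denominator as event-free. The error then runs one way: re-labeling looks rarer, and delabeling more durable, than it is. A larger sample does not reduce it. The 1-year review is the plan's only measure of whether the label stays off, and several of the benefits listed in Section 4.c depend on that.

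**Working it through.** **The plan's own figure.** There is none to reproduce. The documents give no sample size, expected re-labeling rate or share lost to follow-up. Every rate below is an assumption used to show the range.

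**Set-up.** Among delabeled subjects, let
- d = share with no later contact in the record,
- r_stay and r_leave = true 1-year re-labeling rates with and without later contact,
- c = share of re-labels in the no-contact group that still show in the record (0 if none, 1 if all).

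Truth = (1 − d)·r_stay + d·r_leave

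Record, with everyone in the denominator = (1 − d)·r_stay + d·c·r_leave

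Bias = record − truth = −d·(1 − c)·r_leave

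This is never positive. It is zero only if d = 0, c = 1 or r_leave = 0.

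**Size when both groups have the same true rate r.** The record then shows r·(1 − d·(1 − c)).

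| r | d | c = 0 | c = 0.5 | c = 1 |
|---|---|---|---|---|
| 10% | 6% | 9.4% | 9.7% | 10% |
| 10% | 20% | 8.0% | 9.0% | 10% |
| 10% | 30% | 7.0% | 8.5% | 10% |
| 20% | 6% | 18.8% | 19.4% | 20% |
| 20% | 20% | 16.0% | 18.0% | 20% |
| 20% | 30% | 14.0% | 17.0% | 20% |

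With c = 0 the relative shortfall equals d.

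**Where 6% comes from.** Ages 2 to 18 make 17 single years. If subjects were spread evenly over them (an assumption), 1/17 = 5.9% would be 18 at challenge and 19 at the review, past the enrolled range. A subject aged 17 at challenge is 18 at the review and still inside it. Whether the 18-year-olds leave is not stated, and no upper age limit for the clinic is given. The 20% and 30% rows stand for departure for any reason and have no source in the documents.

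**Does restricting the denominator cure it?** Take r_stay = 10%, d = 20%, c = 0:

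| r_leave | Truth = 0.8 × 10% + 0.2 × r_leave | Record, all subjects | Restricted to those with contact |
|---|---|---|---|
| 0% | 8% | 8% | 10% |
| 5% | 9% | 8% | 10% |
| 10% | 10% | 8% | 10% |
| 20% | 12% | 8% | 10% |

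Restriction is exact only when the two groups re-label at the same rate, so it needs bounds beside it. For an illustrative 100 delabeled subjects with 20 unknown and 8 labels among the other 80, the restricted rate is 8/80 = 10%, the lower bound 8/100 = 8%, and the upper bound (8 + 20)/100 = 28%. All four truths above lie between the bounds.

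**The case against.** The strongest reply is that the plan does not do what a critic might attribute to it. Four stronger readings are tempting, and the documents support none of them.

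- **That the record is this clinic's alone, so a child who leaves cannot be re-labeled in it.** Section 4.a speaks only of the electronic medical record. Section 2.b names an allergy clinic of the same organisation; whether it shares the record is not stated. With full capture (c = 1) there is no bias.
- **That the plan scores such children as label off.** No scoring rule or denominator is written. That outcome is what a literal reading of the list would give, so the defect is a missing rule, not a wrong one.
- **That everyone aged 17 or 18 ages out, about 2/17 = 12%.** The clinic enrols 18-year-olds, so those aged 17 at challenge remain in range a year later. At most about 6% pass it under even ages, and some of those may still be seen.
- **That the study's main conclusion is at risk.** Section 1 states the aim as feasibility of risk-stratification and of completing the challenge in primary care. The 1-year review lies outside that aim, and no decision in the plan rests on it.

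A further fair objection is that dropping subjects without contact can overstate re-labeling, as the first two rows of the last table show.

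All of this narrows the point. What remains is that the planned review cannot separate a clear list from an unvisited one, and that any error from pooling them has a known direction.

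**Conclusion.** The concern holds in a limited form. As described, the 1-year review does not distinguish a label that stayed off from a list with no later activity. If the two are pooled, the re-labeling proportion is understated, or unchanged where the record captures all outside re-labels or there are none to miss. A reader should not infer that understatement is certain or that its amount is known, because the reach of the record, the share without later contact and the re-labeling rate are all unstated.

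On the assumptions of no visible re-labels and equal true rates, the shortfall from a true 10% runs from 0.6 percentage points (6% without contact) to 2 points (20% without contact), and it shrinks as capture improves. The result affected is a secondary descriptive one. This is a cheap improvement to that result, not a threat to the feasibility aim.

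**What to change.** In Section 4.a:

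1. State which sites and services the electronic medical record covers.
2. At the 1-year chart review already planned, record the date of the last clinical encounter or allergy-list review after the challenge. Exclude the challenge visit and the study's own 7-10 day call; otherwise nearly every subject reached by that call would qualify.
3. Pre-specify a window before the 1-year date within which that encounter or review must fall, so that a single visit soon after the challenge does not count as 1-year follow-up.
4. Class subjects with none in the window and no label showing as not assessable, and report their number.
5. Report the re-labeling proportion among assessable subjects, with a lower bound (all subjects, unknowns counted as not re-labeled) and an upper bound (all subjects, unknowns counted as re-labeled). Say that the restricted rate is unbiased only if subjects with and without later contact re-label at the same rate.

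The cost is one date field and a few sentences, with no extra visits, calls or staff. The downside is a smaller denominator, a wider interval (about 12% wider at the same proportion if 20 of 100 are not assessable, since √(100/80) = 1.12) and possibly a less favourable stated rate.
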